Saturated solutions of potassium iodide can be used for hyperthyroidism or thyroid storm, as high amounts of iodide temporarily suppress secretion of thyroxine from the thyroid gland.

Ultrasound will be used to take images of thyroid to measure thyroid volumes, as well as take images of the vascular flow in each lobe of the gland.

Using 3D imaging software, we will quantify the vascular flow in the ultrasound images and compare baseline images with the OR images to assess if there is a difference in vascular flow between these timepoints.

Study Subjects

Inclusion criteria: All patients with Graves' disease who will be undergoing total thyroidectomy.

Exclusion criteria: Age less than 18, previous RAI therapy, previous treatment with SSKI.

Our goal recruitment number for this pilot study is 30 patients.

Statistical Analysis

We believe that a decrease in vascularity of at least 10% would be clinically significant. In order to demonstrate this amount of difference, our pilot study would be adequately powered with at least 40 patients to show a difference of 11% between the two treatment arms. Utilizing the program "Power and Sample Size Calculation v 3.0.43", a power analysis was conducted setting type I error at 0.05, Power at 0.8, and an experiment to control arm ratio of 2:1. In order to detect a clinically significant change of 10% vascularity in the gland, 20 patients will need to be included in the experimental arm and 10 patients in the control arm.

References

2. Ansaldo GL, Pretolesi F, Varaldo E, et al Doppler evaluation of intrathyroid arterial resistances during preoperative treatment with Lugol's iodide solution in patients with diffuse

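### The sample-size paragraph asks for 40 patients to show an 11% difference but only 30 to detect a smaller 10% difference; if the 40-patient statement is right, the planned 30 give about 54–60% power, not 80%

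*Combined protocol and SAP*

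**What the plan says.** The combined protocol and SAP justifies its sample size in one short paragraph under Statistical Analysis.

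- The threshold of interest: "We believe that a decrease in vascularity of at least 10% would be clinically significant".
- To demonstrate that amount, the paragraph says "our pilot study would be adequately powered with at least 40 patients to show a difference of 11% between the two treatment arms". It attaches no allocation ratio or power figure to this statement.
- It then reports that "a power analysis was conducted setting type I error at 0.05, Power at 0.8, and an experiment to control arm ratio of 2:1".
- From that calculation it concludes, for a 10% change, that "20 patients will need to be included in the experimental arm and 10 patients in the control arm", which makes 30 in total.

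Under Study Subjects the target matches the second figure: "Our goal recruitment number for this pilot study is 30 patients".

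The plan does not give an SD, the statistical test, whether the type I error is one- or two-sided, or an allowance for patients who cannot be evaluated. It also does not say whether 10% is a relative change from baseline or a number of percentage points.

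**The concern.** Two sample-size requirements stand side by side, and they run in the wrong direction: the larger effect is given the larger sample. With everything else equal, the smaller effect needs more patients. At least one of the two figures must therefore be wrong, or rest on an assumption the paragraph does not disclose.

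This paragraph is the only justification for the trial's size. As it stands, a reader cannot tell whether 30 patients give the stated 80% power for the effect the protocol calls clinically significant, or little better than even odds of detecting it. In the second case a null result would say little about whether SSKI reduces vascularity by 10%, yet the protocol would appear to support reading it as evidence against such an effect.

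The goal of 30 also equals the required 20 + 10 exactly. The endpoint needs both an office scan and an operating-room scan, so a cancelled operation or a missing second scan takes the trial below its own requirement.

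**Working it through.** **Inputs from the protocol (Statistical Analysis and Study Subjects).** Type I error 0.05; power 0.80; ratio 2:1 for the reported power analysis; statement A, at least 40 patients for 11%; statement B, 20 + 10 patients for 10%; recruitment goal 30.

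**Assumptions added here.** Two-sided test; two-sample comparison of means with a common SD; 40 is a total, split either 20:20 or 27:13 (nearest whole numbers to 2:1); 10% and 11% are on the same scale.

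**Can the plan's figures be reproduced?** Not directly, because no SD is given. Each statement can only be solved backwards for the SD it implies.

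**Step 1: a check that needs no SD.** The required total is proportional to (SD/difference)². Going from 11% to 10% multiplies it by (11/10)² = 1.21, so 40 becomes 40 × 1.21 ≈ 48. The protocol goes down to 30. Allocation does not explain this: relative to 1:1, a 2:1 split multiplies the total by (1 + 2)²/(4 × 2) = 1.125, which widens the gap.

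**Step 2: implied SDs.** The standardised difference d detectable at 80% power comes from the noncentral t distribution with n₁ + n₂ − 2 degrees of freedom and noncentrality d/√(1/n₁ + 1/n₂). The implied SD is the stated difference divided by d.

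| Statement | Split | Detectable d | Implied SD |
|---|---|---|---|
| B: 30 patients, 10% | 20:10 | 1.124 | 10/1.124 = 8.90 |
| A: 40 patients, 11% | 20:20 | 0.909 | 11/0.909 = 12.10 |
| A: 40 patients, 11% | 27:13 | 0.971 | 11/0.971 = 11.33 |

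The normal approximation gives about 9.2 for B and 11.6–12.4 for A. The ranges do not overlap under either method.

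**Step 3: if statement A is right.** For the planned 20:10 split:

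| SD | Power for 10% | Detectable at 80% power | Total needed for 10% at 2:1 |
|---|---|---|---|
| 12.10 | 54.0% | 1.124 × 12.10 = 13.6% | 54 |
| 11.33 | 59.5% | 1.124 × 11.33 = 12.7% | 48 |

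**Step 4: if statement B is right.** At SD 8.90, 40 patients have 96.8% power (20:20) or 94.6% power (27:13) for 11%. About 27 patients at 2:1, or 24 at 1:1, would be enough for 11% at 80% power, so a minimum of 40 would be wrong.

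**Step 5: other readings.**
- One-sided 0.05: implied SDs are 10.1 (B) and 12.9–13.7 (A), and power of 20:10 for 10% under A is 57–62%.
- 40 read as the experimental arm of a 40:20 split: about 42–44% power (two-sided).
- 40 read as the number per arm: about 30–31% power (two-sided).

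None of these reconciles the two statements.

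**Step 6: losses (illustration only, since the protocol gives no rate).** At the favourable SD of 8.90, 10% loss (18:9) lowers power from 80% to 75.4%, and 20% loss (16:8) lowers it to 69.9%.

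**The case against.** Three points can be made for the paragraph.

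- **The two figures may describe different quantities.** The 11% is a between-arm difference, while the 10% is worded as a change in the gland and could be a within-patient change from baseline with a different SD. But the 40-patient sentence is introduced as the way to demonstrate the 10% threshold, and the 30 comes from a calculation with an experimental-to-control ratio, which is a two-arm comparison. If two quantities were meant, the text does not say so.
- **Adequate power may mean more than 80%.** The 40-patient sentence carries no power figure, and at SD 8.9 its 95–97% would certainly be adequate. But it gives 40 as a minimum, and 0.8 is the only power stated.
- **This is a pilot, and the 54–60% rests on an SD the protocol never gives.** The pilot label would excuse a modest sample, but not a formal power claim that conflicts with itself.

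Two things stand. The 54–60% is conditional on the 40-patient statement and on the assumptions listed, so it measures the size of the conflict and is not an estimate of the trial's true power. The loss calculation is an illustration, not an expected rate.

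**Conclusion.** The contradiction holds and must be fixed. For a common SD, test, error rate and power it does not depend on the value of the SD: 11% cannot need 40 patients while 10% needs 30.

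Its size does depend on which statement is right, and the text does not settle that. Under the 40-patient statement (two-sided 0.05, 40 as a total), the planned design falls short of its 80% claim by about 20 to 26 percentage points. Under the 30-patient statement the claim stands only if all 20 + 10 patients are evaluable, and the 40-patient sentence is an error.

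**What to change.** Keep the target of 30 and replace the paragraph with one calculation that states:

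- the SD of the vascularity measure and its source;
- the test and whether it is one- or two-sided;
- whether 10% is a relative change from baseline or percentage points, and that the comparison is between arms;
- the power for 10%, or the difference detectable at 80% power, at the expected evaluable number rather than the recruitment target. The 18:9 split shows the format; the sponsor should supply its own expected loss.

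The sourced SD then decides what happens to the 40-patient sentence. If it is about 8.9 or lower, delete the sentence. If it is nearer 11.3–12.1, say plainly that 30 patients give about 54–60% power for 10% before losses and can detect about 12.7–13.6% at 80% power. The sentence should not be removed without that SD, because it may be the only sign in the plan that 30 is too few.

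The cost is protocol wording, and probably a less favourable power or detectable difference. No extra patients are needed. Restoring 80% power for 10% under the 40-patient statement would instead take 48–54 patients at 2:1; this fix does not require that.

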Title:

Does the Use of Pre-operative SSKI Actually Reduce Vascularity and Improve Surgical Outcomes for Total Thyroidectomy in Graves' Disease?

ClinicalTrials.gov ID: NCT04080505

Protocol date: February 23, 2015

Research/Protocol Hypothesis

We hypothesize that the pre-operative use of SSKI (potassium iodide oral solution) reduces the hypervascularity of the thyroid gland in Graves' disease patients undergoing total thyroidectomy, thus reducing blood loss, operative time, and complications.

Scientific Abstract

Patients with Graves' disease who undergo total thyroidectomy are often treated with a 7-14 day pre-operative course of SSKI. This concentrated solution of potassium iodide not only helps to convert patients from a hyperthyroid to euthyroid state, but also is thought to reduce the vascularity of the thyroid gland for surgery. However, there is no published literature evaluating whether there is a true quantitative decrease in vascularity with SSKI treatment. In this prospective, randomized study, we aim to quantify if there is any change in vascular flow with SSKI treatment and if this difference results in a clinically significant difference in surgical outcomes.

Methods

Patients will be randomized into two treatment groups – those who receive SSKI for 7 days before surgery and those who do not. To assess vascular flow within the thyroid gland, all patients will get a baseline neck ultrasound when evaluated in the office, as well as a second ultrasound in the operating room before surgery. Using 3D imaging software, we will quantify the vascular flow in the ultrasound images and compare baseline images with the OR images to assess if there is a difference in vascular flow between these timepoints. Other endpoints we will measure are: estimated blood loss in surgery, total operative time, postoperative complications including rates of recurrent laryngeal nerve injury, hypoparathyroidism, hematoma, infection rates.

Study Description

Study Purpose and Rationale

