Patients with Graves' disease and goiters tend to have very vascular thyroid glands, which increases operative bleeding risks/rates. Many surgeons treat these patients with preoperative SSKI which is believed to decrease the vascularity, which in turn may decrease bleeding risks. However, there has been no quantitative data published on whether this is a real effect with true clinical benefit, in either animal or human models with SSKI. There have been some studies in Europe studying Lugol's solution, a different formulation of iodine, which show some decreased vascularity using color Doppler or measurements of CD34 cells (1,2).

Study Design & Procedures

All patients would receive a baseline neck ultrasound on our initial office consultation. We do our own office ultrasounds to assess the pathology ourselves. In this study we would standardize all patients to have a baseline ultrasound with us to obtain vascular flow imaging no less than 7 days prior to surgery.

Patients would be randomized to either receive 7 days of pre-operative SSKI or not receive any drug (in our current practice at Columbia, all patients with Graves' disease receive SSKI pre-operatively, though this is not standard practice across the country, thus the 'no drug' group would be experimental for research). Prescriptions will be written by the surgeon and filled by the patient at an outside pharmacy.

All patients would receive a second ultrasound on the operating table before surgery to assess for change in vascularity (experimental, as not all patients receive intra-operative ultrasounds before surgery). Both ultrasounds are performed by the surgeon and there is no additional charge for this test.

We would record estimated blood loss, operative length, and other complication rates such as recurrent laryngeal nerve injury, hypoparathyroidism, hematoma, infection (these rates are already recorded for all patients).

Any post-operative procedures and data collection will be standard of care. We will review consented patients' chart if there are any post-op complications. If there are no complications, the data collection will be complete at their post-op appointment.

Study Drugs or Devices

SSKI is potassium iodide oral solution. It is a concentrated form of potassium iodide containing 1g/ml. It is commonly used for lung conditions such as emphysema, bronchitis and works as an expectorant. It works by thinning mucous secretions (phlegm) in the lungs.

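### Does the unexplained 2:1 split, with arms of 20 and 10 not named by treatment, call for a change to the plan?

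*Combined protocol and SAP*

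**What the plan says.** The Statistical Analysis section reports a power calculation run by "setting type I error at 0.05, Power at 0.8, and an experiment to control arm ratio of 2:1". It concludes that "20 patients will need to be included in the experimental arm and 10 patients in the control arm", which matches the total under Study Subjects: "Our goal recruitment number for this pilot study is 30 patients". Neither place names the treatment in each arm or explains the ratio. The descriptions of randomisation in Methods and in Study Design & Procedures give two groups and no ratio.

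Two other places bear on the labels. Study Design & Procedures notes that SSKI is the site's current practice, "thus the 'no drug' group would be experimental for research". The Research/Protocol Hypothesis makes SSKI the intervention under test: "We hypothesize that the pre-operative use of SSKI (potassium iodide oral solution) reduces the hypervascularity of the thyroid gland".

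**The concern.** There are two points.

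- **Ratio.** For a fixed total and equal SDs, equal allocation gives the smallest variance for a difference in means. A trial of 30 has little precision to spare, and 2:1 gives some up with no stated return.
- **Labels.** If the remark in Study Design & Procedures is taken as an arm name, 20 patients go without SSKI and 10 receive it. If the hypothesis is the guide, the numbers swap. Two statisticians could build opposite randomisation lists. The choice decides how many patients forgo the site's usual preparation and which arm's change from baseline is estimated more tightly.

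**Working it through.** **Inputs.** From Statistical Analysis: type I error 0.05, power 0.80, ratio 2:1, arms of 20 and 10, effect 10%. From Study Subjects: total 30. Not given: SD, sidedness, and whether 10% means percentage points. Assumed here: a two-sample t-test, equal SDs and 10 points; two-sided unless noted.

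**1. The plan's own figure.** Without an SD, 20 + 10 cannot be derived forwards. Solving backwards (noncentral t), 20:10 has 80% power for 10 points when the SD is 8.90 (two-sided) or 10.13 (one-sided). The stated sizes are therefore attainable at 2:1, but not confirmed.

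**2. Cost of the ratio, free of the SD.** Variance of the difference = SD² × (1/n₁ + 1/n₂).

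- 20:10: 1/20 + 1/10 = 0.150, so SE = 0.387 SD
- 15:15: 1/15 + 1/15 = 0.133, so SE = 0.365 SD
- Variance ratio 0.150/0.1333 = 1.125; SE ratio √1.125 = 1.061

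The difference detectable at 80% power is 1.124 SD at 20:10 and 1.060 SD at 15:15. At SD 8.90 that is 10.0 and 9.4 points.

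**3. Power for 10 points, total of 30.**

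| Assumed SD | 20:10 | 15:15 | Gain |
|---|---|---|---|
| 7 | 0.945 | 0.965 | 0.020 |
| 8 | 0.876 | 0.910 | 0.034 |
| 8.90 | 0.800 | 0.844 | 0.044 |
| 10 | 0.703 | 0.753 | 0.050 |
| 12 | 0.547 | 0.596 | 0.049 |
| 15 | 0.383 | 0.422 | 0.039 |

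One-sided, at SD 10.13, the figures are 0.800 and 0.839. In patients: at SD 8.90, 14 per arm gives 0.817 and 13 per arm gives 0.785. So 1:1 needs 28 patients where 2:1 needs 30, a saving of two.

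**4. Unequal SDs.** Let s₁ be the SD in the larger arm. The two designs tie when s₁²/20 + s₂²/10 = (s₁² + s₂²)/15. That reduces to s₂²/30 = s₁²/60, so s₁/s₂ = √2 = 1.41. At s₁/s₂ = 1.5 the variance terms are 0.2125 (2:1) and 0.2167 (1:1), so 2:1 is already slightly better. At s₁/s₂ = 0.5 they are 0.1125 and 0.0833, so 2:1 is worse by a factor of 1.35. The document gives no basis for choosing among these cases.

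**5. What 1:1 gives up.** The 95% half-width for an arm's own mean change is t × SD/√n. At SD 8.896:

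- n = 20: 2.093 × 8.896/√20 = 4.2 points
- n = 15: 2.145 × 8.896/√15 = 4.9 points
- n = 10: 2.262 × 8.896/√10 = 6.4 points

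Moving to 15:15 widens the larger arm's interval from 4.2 to 4.9 and narrows the smaller arm's from 6.4 to 4.9. The no-SSKI count becomes 15: five fewer if that arm was to have 20, five more if it was to have 10.

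**6. Labels.** Study Design & Procedures uses the word experimental twice: for the no-drug group, and for the ultrasound done just before the operation. Both times the reason given is departure from routine practice at the site. The word marks what is not usual care; it does not define an arm. The sentence therefore does not firmly assign 20 patients to no drug. Swapping the arms leaves 1/20 + 1/10 unchanged, so with equal SDs between-arm power is 0.800 either way.

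**The case for a change.** The strongest case for a change is that 1:1 costs no extra patients, that no reason for 2:1 appears anywhere, and that a list cannot be produced until someone says which treatment has 20. The variance arithmetic is right, and the silence on the ratio is real.

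The case can be pressed with the document's other sizing statement, that the study would be "adequately powered with at least 40 patients to show a difference of 11% between the two treatment arms". For 80% power that implies an SD of 12.10 if split 20:20, or 11.33 if split 27:13. With 30 patients and a 10-point effect, power at 20:10 is then 0.540 or 0.595, against 0.589 or 0.645 at 15:15. But both allocations miss 80% by a wide margin at those SDs. The shortfall comes from the SD and the total, and the ratio neither causes it nor cures it. The conflict between 30 and 40 patients is a separate and larger matter.

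Nor is 2:1 plainly without return. The Scientific Abstract aims to quantify change in flow under SSKI, and Methods compares each patient's two scans. If SSKI is the larger arm, 2:1 sharpens that estimate. The plan does not give this as its reason, so it shows only that a sensible reason is available.

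What stands is that the ratio is unexplained and that each arm's size has to be attached to a treatment before patients are randomised.

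**Conclusion.** No change to the plan follows. The power calculation was done at the 2:1 ratio the plan uses, and no stated target is missed because of that ratio. Equal allocation would gain 2 to 5 percentage points of power over SDs of 7 to 15, or save two patients at the back-solved SD. In exchange it loosens the larger arm's own estimate and shifts the number without SSKI by five, in a direction that depends on the intended mapping. The gain rests on roughly equal SDs, and the point-scale figures also on reading 10% as 10 points. Only the 12.5% variance ratio and the 1.12 versus 1.06 SD comparison do not depend on the size of the common SD.

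The labels are ambiguous, not contradictory in a way that damages the analysis. Either mapping gives a valid randomised comparison, with the same between-arm power if SDs are equal. The sponsor knows which arm was meant, and the randomisation list will record it by treatment. This note takes no view on which mapping is right.
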